## Study Protocol and Statistical Analysis Plan

# Cryoballoon Ablation Versus Medical Therapy in Patients with Atrial Fibrillation and Heart Failure with Different Ejection Fraction Categories

### 1. Study objective

This study is to assess the effectiveness and safety of cryoballoon ablation comparing with medical therapy in patients with atrial fibrillation and heart failure with different ejection fraction categories

### 2. Study Design

Study Type	Interventional (Clinical Trial)
Estimated Enrollment:	200 participants
Allocation:	No-Randomized
Intervention Model:	Parallel Assignment
Primary Purpose:	Treatment
Estimated Study Start Date:	May 1,2022
Estimated Primary Completion Date:	December 31, 2023
Estimated Study Completion Date:	June 1, 2024

### 3. Study subjects

Subjects with atrial fibrillation and heart failure with different ejection fraction categories are divided to either an anti-arrhythmic drug or cryoballoon catheter pulmonary vein isolation.

(1) Medical treatment group: receive class I or class III AAD to restore or maintain sinus rhythm; Antiarrhythmic drug including Propafenone, Sotalol, Dronedaron and

Amiodarone;

(2) Experimental: cryoballoon ablation group receive cryoballoon ablation to restore sinus rhythm; Pulmonary vein isolation by cryoballoon ablation using Medtronic Arctic Front Advance™ Cardiac CryoAblation Catheters (23mm and 28mm);

#### **4. Eligibility Criteria**

##### **➤ Inclusion Criteria:**

- (1) Diagnosed with symptomatic paroxysmal or persistent atrial fibrillation: defined as at least two symptomatic episodes in the last six months prior to enrollment.
- (2) At least 18 years old and not older than 80 years old.
- (3) Able and willing to give informed consent.

##### **➤ Exclusion Criteria:**

- (1) History of AF treatment with class I or III AAD, including sotalol, with the intention to prevent an AF recurrence. However, patients pretreated with above AAD for less than 7 days with the intention to convert an AF episode are allowed;
- (2) Previous left atrial ablation;
- (3) Previous cardiac surgery including prosthetic valves;
- (4) Permanent pacemaker or defibrillator implant;
- (5) Second degree type II or third-degree AV-block or a pattern of left/right bundle branch block;
- (6) History of previous myocardial infarction or percutaneous intervention during the last 3 months;
- (7) Any history of previous transient ischemic attack, prolonged reversible ischemic neurological deficit, and/or stroke;
- (8) Known intracardiac thrombus formation;
- (9) Pulmonary vein stent;
- (10) Known cryoglobulinaemia;
- (11) Active systemic infection;
- (12) Hypertrophic cardiomyopathy;
- (13) Life expectancy is  $\leq 1$  year;
- (14) Reversible cause of atrial fibrillation (eg, hyperthyroidism or alcoholism);
- (15) Abnormal long or short QT intervals, signs of Brugada syndrome, known family history of inherited ion channel disease, and/or arrhythmogenic right ventricular dysplasia;

- 
- (16) Chronic obstructive pulmonary disease with detected pulmonary hypertension and/or any other evidence of significant lung disease;
  - (17) Contraindication for oral anticoagulation;
  - (18) Pregnant women or woman of childbearing potential with inadequate birth control;
  - (19) Women who are breastfeeding;
  - (20) Any significant congenital heart defect corrected or not corrected; however, patent foramen ovale is allowed;
  - (21) Thrombocytosis (platelet count > 600,000 / $\mu$ L) or thrombocytopenia (platelet count < 100,000 / $\mu$ L);
  - (22) Untreated or uncontrolled hyperthyroidism or hypothyroidism;
  - (23) Renal dysfunction with glomerular filtration rate < 60 mL/min;
  - (24) Unstable angina pectoris;
  - (25) Symptomatic carotid stenosis;
  - (26) Myxoma based on laboratory abnormalities;
  - (27) Sarcoidosis;
  - (28) Unwilling to unable to comply with the study procedure and follow-up schedule due to any disease condition;
  - (29) Legal incapacity or evidence that the patient cannot understand the purpose and risks of the study, including inability to comply fully with study procedures and follow-up;
  - (30) Employed by Medtronic, or the department of an investigator, or close-familial relative of an investigator;
  - (31) Enrolled or planning to participate in a potentially confounding drug or device trial during this study.

## **5. Study Process**

### **5.1 Medical treatment group**

Patients admitted to the medical treatment group after screening could receive electrocardiography and receive class I or class III AAD to restore or maintain sinus rhythm. The survey included variables that concern the baseline characteristics of patients, including risk factors, clinical history, cardiac diagnosis, electrocardiogram, echocardiography, laboratory blood tests, and treatments. All patients were symptomatic (functional NYHA class II–IV) and were treated according to contemporary clinical guidelines.

## 5.2 Cryoballoon ablation group

### ➤ Pre-procedure

In addition to survey contents for medical treatment group, the Transesophageal echocardiography (TEE) was performed in all patients prior to the procedure. The echocardiographic parameters include left ventricular ejection fraction (LVEF), peak early trans-mitral inflow velocity/peak late mitral inflow velocity ratio (E/A), left atrial diameter (LAD), LV end-diastolic diameter (LVEDD), and LV mass. All recordings were performed and analyzed by the same investigator. In patients on vitamin K antagonists, anticoagulation was continued throughout the procedure, aiming at an international normalized ratio (INR) of 2-3. In patients treated with novel oral anticoagulants (NOACs), the drug was discontinued 12-24 hour prior to the procedure and re-initiated 6-hour post-ablation at half the regular dose, and then at full dose on the following day.

### ➤ Procedure

All procedures were performed under deep sedation using midazolam, fentanyl, and propofol. A single trans-septal puncture was performed via the right femoral vein under fluoroscopic guidance. Heparin was administered after trans-septal puncture to maintain an activated clotting time ranging from 250 - 350s. In order to identify all PV ostia, selective PV angiography was performed. The second-generation 28-mm CB was advanced into the LA via the 12Fr steerable sheath and a spiral mapping catheter (20-mm diameter; Achieve, Medtronic, Inc.) was advanced into the target PV to record electrical activity. In patients demonstrating AF at the time of the procedure, electrical cardioversion was performed after the final freeze-cycle and PVI was reconfirmed in SR. Phrenic nerve capture was monitored by intermittent fluoroscopy and by tactile feedback of diaphragmatic contraction by the operator's hand positioned on the patient's abdomen. The procedure-related complications such as bleeding, phrenic nerve palsy (PNP), cerebral embolism, pericardial effusion/ tamponade or atrioesophageal fistula were evaluated.

➤ **Post-procedure**

Following ablation, low-molecular-weight heparin was administered to patients on vitamin K antagonists and an INR <2.0 until a therapeutic INR of 2–3 was achieved. NOACs were re-initiated 6 h post-ablation. Anticoagulation was recommended for at least 3 months and thereafter according to the individual CHA2DS2-VASc scores. Previously ineffective antiarrhythmic drugs were continued for 3 months post-ablation. All patients were treated with proton-pump inhibitors for 6 weeks. All patients were treated with optimal medical treatment according to the latest guidelines.

Post-ablation, all patients had in-office Follow-up visit at discharge. A subset of patients reconsented for 1, 3, 6, and 12-month follow-up visits. On follow-up visits physical examination was performed, a 12-lead electrocardio gram (ECG) and 24-h Holter monitor were recorded, and medication changes were documented. In addition, regular telephone interviews were performed. Additional outpatient clinic visits were immediately initiated in cases of symptoms suggestive of recurrent arrhythmia. Repeat ablation was offered to the patient in cases of symptomatic AF/AT recurrence after the blanking period or symptomatic drug-refractory recurrent AF/AT within the blanking period that could not be managed without intervention. Furthermore, LVEF and the NYHA score were systematically evaluated at follow-up on TTE.

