## **6. Outcome Measures**

➤ **Primary Outcome Measures:**

(1) Treatment success at one year

Treatment success at 12 months after antiarrhythmic drug (AAD) initiation or ablation utilizing cryoballoon catheter measured by freedom from AF recurrence following a 3-month period after the index ablation or AAD initiation.

The primary outcome was time to first documented recurrence of symptomatic or asymptomatic atrial tachyarrhythmia (AF, atrial flutter, or atrial tachycardia)

(2) Rate of serious adverse events

Rate of complications and adverse events occurred during cryoballoon ablation and postoperative follow-up, including procedure-related complications such as bleeding, phrenic nerve palsy (PNP), cerebral embolism, pericardial effusion/tamponade, atriopharyngeal fistula, and all-cause mortality, re-hospitalization for HF, and the composite event of all-cause mortality or HF hospitalization.

➤ **Secondary Outcome Measures**

(1) Quality of life changes at 12 months measured by AF Quality of Life Survey (AFEQT)

The improvement in quality of life between baseline and 12 months after the index ablation procedure or AAD measured by AFEQT is evaluated.

(2) Quality of life changes at 12 months measured by 12-Item Short Form Survey (SF-12)

The improvement in quality of life between baseline and 12 months after the index ablation procedure or AAD measured by SF-12 is evaluated.

(3) Arrhythmia recurrence during blanking period (Time Frame: 3 months)

Atrial tachycardia recurrence rate during the blanking period is evaluated.

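### Ascertainment of primary outcome (2) after discharge is neither universal in the ablation group nor shown to be equal between the two groups

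*Combined protocol and SAP*

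**What the plan says.** Section 5.2 (Post-procedure) gives the whole ablation group one scheduled visit and restricts the later ones: "all patients had in-office Follow-up visit at discharge. A subset of patients reconsented for 1, 3, 6, and 12-month follow-up visits". The size of the subset, how it was chosen and when its members re-consented are not stated.

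The content of the visits is given as follows: "On follow-up visits physical examination was performed, a 12-lead electrocardio gram (ECG) and 24-h Holter monitor were recorded, and medication changes were documented". LVEF and NYHA class were also assessed. Vital status, hospital admissions and adverse events are not on the list.

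Two other kinds of contact are mentioned. One is by telephone: "In addition, regular telephone interviews were performed". No dates, questions or population are given for these calls. The other is unscheduled clinic visits, which are triggered only by symptoms of returning arrhythmia.

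Section 5.1 describes what was collected at baseline in the drug group. It sets no visits or calls afterwards.

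Section 6, primary outcome (2), covers complications during ablation and in the period after it, and includes "all-cause mortality, re-hospitalization for HF, and the composite event of all-cause mortality or HF hospitalization". It has no end time. Section 7 plans Cox models for adverse outcomes by EF category, but gives no censoring rule, no denominator and no handling of patients without follow-up visits.

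**The concern.** Death and HF re-hospitalisation are largely events of the period after discharge, and a re-hospitalisation can occur only then. A rate of such events needs the same enquiry, over the same period, for every patient in the denominator. As written, the plan schedules later visits only for ablation patients who agreed a second time, lists no safety enquiry at those visits, and schedules nothing for the drug group.

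The objective in Section 1 is to compare effectiveness and safety between the two treatments. If events are found more readily in one group than in the other, the difference in observed rates mixes the treatment effect with the difference in capture. Without a record of who was contacted and when, no later analysis can separate the two. A late complication could also go unrecorded in an ablation patient who has no scheduled visit.

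**Working it through.** **Figures in the plan.** There is none to reproduce. The plan states 200 participants in total, with no split by group, no expected event rate and no expected re-consent share. The inputs below are assumptions, marked as such.

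**What the outcome needs against what is scheduled.**

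- Vital status and admissions for all ablation patients to a common time: the only universal scheduled visit is at discharge.
- The same for all drug patients: nothing is scheduled.
- A safety enquiry at each contact: none is listed for the visits, and the content of the calls is not given.
- A last-contact date for each event-free patient, which a Cox model requires: no rule is given.

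**Case A: all ablated patients are the denominator and unobserved patients count as event-free.** Let *s* be the re-consent share, *p* the true rate (taken as equal in both parts), and *c* the share of events captured outside the subset. Capture inside the subset is assumed complete, which is generous given the listed visit content.

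Observed rate = *s* × *p* + (1 − *s*) × *p* × *c*, with *p* = 20%:

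- *s* = 0.5, *c* = 0: 0.5 × 20% = 10%
- *s* = 0.5, *c* = 0.5: 10% + 0.5 × 20% × 0.5 = 15%
- *s* = 0.8, *c* = 0: 0.8 × 20% = 16%
- *s* = 0.8, *c* = 0.5: 16% + 0.2 × 20% × 0.5 = 18%

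The shortfall, (1 − *s*) × *p* × (1 − *c*), is never negative. Counting unobserved patients as event-free can only lower a group's rate.

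**Case B: only the subset is analysed.** Let the true rates be *p*₁ in the subset and *p*₀ outside it. The bias is *p*₁ − [*s* × *p*₁ + (1 − *s*) × *p*₀] = (1 − *s*) × (*p*₁ − *p*₀). Its sign is that of *p*₁ − *p*₀. With *s* = 0.5 and assumed rates of 15% inside and 25% outside, it is 0.5 × (−10) = −5 percentage points. With the two rates exchanged it is +5.

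**Comparison between groups.** Overall capture in the ablation group under Case A is *s* + (1 − *s*) × *c*: 50 to 75% at *s* = 0.5, and 80 to 90% at *s* = 0.8. If the true rate is 20% in both groups, complete capture in the drug group makes ablation look safer by 5 to 10 points at *s* = 0.5. If the drug group's capture were 40%, its observed rate would be 0.4 × 20% = 8%, and ablation would look worse by 2 to 7 points (10 to 15% against 8%). The sign turns on which group has the better capture, and the documents do not say.

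**Bounds with no information on the rest.** With rate *q* among those seen, the group rate lies between *s* × *q* and *s* × *q* + (1 − *s*). With *q* = 10% assumed, this is 5 to 55% at *s* = 50%, 7 to 37% at *s* = 70%, and 9 to 19% at *s* = 90%. The width is always 1 − *s*.

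**Rare complications.** For an assumed 2% complication and an assumed 100 ablation patients, the chance of seeing no case is 0.98^100 = 13% if all are followed, 0.98^70 = 24% if 70 are, and 0.98^50 = 36% if 50 are.

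**The case against.** The strongest reply is that patients were contacted after discharge. The telephone interviews are described as regular and are not limited to the subset, symptom-triggered visits existed, and Section 5.2 (Procedure) says that procedure-related complications were evaluated. Calls that reached everyone and asked about deaths and admissions could have captured most events. This stands so far as it goes: the text does not show that events were missed. Nor does it show that they were captured, because it says neither who was called nor what was asked, and it places the calls under the ablation group only.

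Four stronger readings are tempting, and the documents do not support them.

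- *The ablation rate must be too low whichever denominator is used.* Case A lowers the rate only to the extent that calls and other contacts missed events. In Case B the direction depends on who re-consented. Survivors and healthier patients may predominate, but symptomatic patients may equally be the more willing to return.
- *Ablation gains 5 to 10 points from follow-up alone.* That presumes complete capture in the drug group, for which Section 5.1 schedules no follow-up at all.
- *Patients who died or were badly harmed could not enter the subset.* That needs re-consent to have followed the procedure. This is a fair inference from the wording, which opens by referring to the time after ablation, but the timing is not stated.
- *The plan's own precautions mark a period of risk.* Section 5.2 says "All patients were treated with proton-pump inhibitors for 6 weeks" and "Anticoagulation was recommended for at least 3 months and thereafter according to the individual CHA2DS2-VASc scores", but gives no reason for the former and ties neither to a named late complication. The argument is not needed, because primary outcome (2) already extends beyond the procedure.

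**Conclusion.** The concern holds as one of incomplete and possibly unequal ascertainment of a primary outcome. It is more than missing detail: the follow-up rule, applied as written, leaves scheduled visits after discharge to a self-selected part of one group and to no one in the other, and the analysis section does not repair this.

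The size cannot be derived from the documents. The observed rates of 10 to 15% and 16 to 18% against a true 20% show what incomplete capture could do in the ablation group. They rest on an assumed event rate, assumed re-consent shares of 50% and 80%, full capture in the subset, the same true rate inside and outside it, and 0 to 50% capture in the rest. They are not estimates for this trial. The direction of the between-group bias is unknown.

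**What to change.** - Take consent for 12-month safety follow-up at enrolment, so that it does not depend on a second agreement.
- Apply the telephone interviews to every patient in both groups at 1, 3, 6 and 12 months, with one fixed script: vital status, any admission and its reason, stroke or TIA, bleeding, and symptoms of the complications named in Section 6. Confirm reported admissions from hospital records.
- Analyse primary outcome (2) in all enrolled patients, with censoring at last confirmed contact and a stated 12-month window.
- Report the re-consent share and the completeness of follow-up by group. Do not base the safety rate on the re-consented subset.
- If follow-up has already ended, as the past tense of Section 5.2 may suggest, ascertain vital status and admissions for all patients as far as consent permits, and report the size of the subset.

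The cost is consent wording, a short script and modest coordinator time. On the text, the drug-group calls and the record checks are new work, not an extension of calls already made. Censoring at last contact leaves residual bias if loss of contact is related to outcome, which is why completeness must be shown by group. No treatment rule changes.

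### After the discharge visit, the only scheduled rhythm recordings in the plan are for ablation patients who re-consent, yet the primary outcome counts documented asymptomatic recurrence to 12 months in both groups

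*Combined protocol and SAP*

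**What the plan says.** **Ablation group (section 5.2, Post-procedure).** "Post-ablation, all patients had in-office Follow-up visit at discharge". The next sentence is: "A subset of patients reconsented for 1, 3, 6, and 12-month follow-up visits". The size of the subset, how it was chosen and when re-consent was sought are not given. Recordings belong to visits: "On follow-up visits physical examination was performed, a 12-lead electrocardio gram (ECG) and 24-h Holter monitor were recorded". Two further contacts are not limited to the subset: "In addition, regular telephone interviews were performed" and "Additional outpatient clinic visits were immediately initiated in cases of symptoms suggestive of recurrent arrhythmia".

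**Medical group (section 5.1).** "Patients admitted to the medical treatment group after screening could receive electrocardiography and receive class I or class III AAD". The wording is permissive and carries no date. The survey that follows lists baseline variables. The section describes no follow-up visit, ECG or Holter.

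**Outcome (section 6, primary outcome 1).** Success is judged 12 months after ablation or drug initiation, following a 3-month blanking period. The event is the first documented atrial tachyarrhythmia, whether or not it causes symptoms.

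**Analysis (section 7).** There is no rule for censoring, and none for patients who lack recordings.

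**Elsewhere.** Exclusion (28) removes patients who cannot "comply with the study procedure and follow-up schedule due to any disease condition". Section 6 also has AFEQT and SF-12 changes at 12 months for both treatments.

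**The concern.** A silent recurrence enters this endpoint only if a recording happens to catch it. The discharge visit cannot supply that recording, because it normally falls inside the blanking period. After it, the plan as written looks for silent recurrence on a schedule in only one part of one group.

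Two distortions follow. Between groups, the chance that the same silent event is counted depends on treatment. Within the ablation group, it depends on whether the patient agreed to come back, which may be related to how the patient was doing. Re-consent appears to come after treatment, but the text does not date it. Allocation is not randomised, so the design offers no protection against either.

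Without a censoring rule, a patient who was never recorded can pass silently into the analysis as a 12-month success. A reader of the results could not tell.

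**Working it through.** **Step 1: who is recorded after month 3, as written.**

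| Patients | Scheduled ECG/Holter | Telephone | Symptom-triggered visit |
|---|---|---|---|
| Ablation, re-consented | months 6 and 12, plus month 3 at the boundary | yes | yes |
| Ablation, others | none written | yes | yes |
| Medical | none written | none written | none written |

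Only the scheduled column can be relied on to find silent recurrence.

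**Step 2: how much the schedule can see.** From month 3 to month 12 is about 274 days. Two Holter days cover 2/274 = 0.7%; three cover 3/274 = 1.1%. Section 4 admits patients "Diagnosed with symptomatic paroxysmal or persistent atrial fibrillation". Capture of short paroxysms may therefore be low. A sustained arrhythmia is easier to catch, so higher capture cannot be excluded.

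**Step 3: illustration with no true difference.** The plan has no figure of its own to reproduce. From the documents come only the total of 200 (section 2) and the two-sided 0.05 level (section 7). Everything else is assumed:
- 100 patients per group
- true recurrence 40% in both groups
- asymptomatic share a = 0.3 or 0.5
- all symptomatic recurrence documented in both groups
- c = share of silent recurrences caught in recorded patients
- f = fraction of the group recorded on schedule: 0.5 for ablation, 0 for medical

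Observed recurrence = 0.40 × [(1 − a) + a × c × f].

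For a = 0.5 and c = 0.7: ablation 0.40 × (0.5 + 0.5 × 0.7 × 0.5) = 27.0%; medical 0.40 × 0.5 = 20.0%; difference 7.0 points.

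Rejection is by exact binomial enumeration of the uncorrected chi-square test. Section 7 lists chi-square among its between-group tests but does not name it as the primary analysis. When both groups have the same observed rate, between 20% and 40%, the test rejects in 4.9-5.1% of trials.

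| Capture c | Observed, a = 0.3 (ablation vs medical) | Observed, a = 0.5 | False difference, points | Rejection |
|---|---|---|---|---|
| 10% | 28.6% vs 28.0% | 21.0% vs 20.0% | 0.6-1.0 | 5.1-5.5% |
| 30% | 29.8% vs 28.0% | 23.0% vs 20.0% | 1.8-3.0 | 6.0-8.2% |
| 50% | 31.0% vs 28.0% | 25.0% vs 20.0% | 3.0-5.0 | 7.6-13.5% |
| 70% | 32.2% vs 28.0% | 27.0% vs 20.0% | 4.2-7.0 | 10.1-21.4% |

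Here the false difference counts against ablation.

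**Step 4: direction.** Suppose instead that every medical patient was recorded and half the ablation group was. Section 5.1 does not say this; the case is shown only because actual practice is unknown. The point differences are the same but favour ablation, with rejection of 5.2-5.4% at 10% capture and 9.6-19.2% at 70%.

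**Step 5: why a best/worst case cannot be the main sensitivity analysis.** Take a = 0.3 and c = 0.3 in step 3. Counting every unrecorded, event-free medical patient as a recurrence gives 100% (medical) against 29.8% (ablation). The reverse switches 50 × 0.72 = 36 ablation patients: 28% (medical) against 29.8% + 36% = 65.8% (ablation). The sign must flip, so the analysis shows only how much is unrecorded.

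**The case against.** **The medical group may have been followed, and section 5.1 merely fails to say so.** This is a fair reading. Exclusion (28) refers to a follow-up schedule, and two questionnaires are due at 12 months in both groups. A reader might infer from section 5.1 that medical patients had no rhythm follow-up at all; the documents do not support that. Equally, a questionnaire or a general mention of a schedule is not a rhythm recording. The visit schedule sits in section 5.2 and opens with ablation, so it cannot simply be read across. Even if it could, it would still bind only a subset.

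**The size may be trivial.** This stands at low capture. At 10% the rejection rate is essentially nominal, and the larger figures need both high capture and a large asymptomatic share. The illustration also assumes that symptomatic recurrence is fully found in both groups, although symptom-triggered visits are written only in section 5.2.

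**Patients outside the subset are not lost.** Correct. A reader might treat them as wholly unobserved and compute very wide bounds on ablation success. Section 5.2 does not support that, because telephone and symptom-triggered contact are not restricted to the subset.

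**Follow-up may be over.** Sections 5 and 7 use the past tense, and section 2 estimates completion on June 1, 2024. That limits what can still be changed in conduct. It does not affect the analysis and reporting.

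**Conclusion.** The concern holds. As written, silent recurrence is sought on a schedule only in re-consenting ablation patients, the primary outcome counts it in everyone, and section 7 does not say how unrecorded time is treated. It must be fixed because it bears directly on the primary comparison and the core repair is cheap.

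Confidence is high for the gap in the text only. On assumed inputs the effect ranges from negligible to material, as tabulated. It would be wrong to cite 21.4% as this trial's false-positive rate, or to say that the bias runs against ablation. Both rest on assumptions about the subset, the capture rate and the medical group's follow-up that the documents do not settle.

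**What to change.** **(1) In any case.** In section 7:
- Keep all treated patients in the analysis set.
- Censor patients without documented recurrence at their last rhythm recording (ECG or Holter), by the same rule in both groups. Do not count unrecorded time as success.
- Report the number and timing of recordings by group, and the number and baseline features of patients with no recording after month 3.
- Add a sensitivity analysis on symptomatic documented recurrence only, where both groups had symptom-triggered contact.
- Add a second over a graded range of assumed undetected recurrence in unrecorded patients, with the best/worst case shown only as an outer bound.
- Limit the conclusion on asymptomatic recurrence if recording differs materially between groups.

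In section 5.1, state what rhythm follow-up the medical group had. Keep the subset sentence in section 5.2 if it describes what was done.

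*Cost:* extra tables and analyses and a few sentences; fewer patient-months at risk and possibly wide intervals. Censoring at the last recording does not remove self-selection. If one group turns out to have little beyond symptom-triggered recordings, its time at risk will be thin and dominated by patients who recurred. The limit on the conclusion then applies.

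**(2) Only if follow-up is still ahead.** Put 12-month follow-up into the enrolment consent, and apply the protocol's existing ECG/24-h Holter schedule and contacts to all patients in both groups, timed from index ablation or drug initiation.

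*Cost:* an amendment, consent wording, and additional visits for medical patients and for ablation patients outside the subset.
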